## **Provide the scientific or scholarly rationale for the research and describe the relevant background information and the specific gaps in current knowledge that this study intends to address:**

One in six people will have a stroke; over half will incur chronic upper extremity (UE) impairment [1–3]. While intensive rehabilitation reduces impairment[4–9], most individuals do not perform enough movement practice [4,5] in the critical window early after stroke when plasticity is heightened. A key reason is that inpatient rehabilitation is focused on achieving the functions needed to return-to-home: transferring, toileting, dressing, and other forms of self-care. This is what health care payors demand: discharge as quickly as possible, preferably to the home. And yet, ironically, in teaching patients compensatory strategies for achieving daily function, true UE recovery is likely bottlenecked. Our working hypothesis is that there is a threshold level of UE motor drive needed to provoke true UE recovery[6], yet individuals with stroke do not routinely exceed this threshold during current inpatient rehabilitation practice.

To remove this bottleneck, Flint Rehab and UC Irvine propose to develop and test a novel device for enabling individuals with severe arm impairment to substantially increase UE motor drive early after stroke “in situ”. We will leverage a ubiquitous piece of technology – the manual wheelchair – based on two key observations. The first is a pivotal study by Feys et al. [7,8] that had patients with subacute stroke (N=100) rock themselves in rocking chairs by repetitively reaching forward to press against a rail, with patients performing about 500-1000 reaches per day[7]; these patients had a significantly greater increase in UE Fugl-Meyer (FM) score of 17 points at a five-year follow up compared to a control group who were passively rocked[8]. This is a remarkable effect, five times the effect of most robotic arm therapy studies, and yet this “rocking therapy” remains unimplemented in routine clinical practice. A critical question then, is, how do we routinely implement such rocking therapy? This leads to the second observation: approximately 70% of stroke inpatients (and nearly 100% of those with severe impairments) spend several hours each day sitting passively in manual wheelchairs, often with their paretic arm statically strapped into an arm trough. Further, when they ambulate in their chair, they are pushed, or taught to ambulate with their “good” arm and leg (note again: function is prioritized over true recovery). What if patients could use “wheelchair time” to practice “rocking therapy”, without needing to transfer to a rocking chair and without requiring direct therapist supervision? That is, what if we gave patients and therapists a novel tool that allowed them to collaborate in generating plasticity-inducing levels of UE motor drive outside of formal treatment time?

We have already demonstrated the feasibility and preliminary clinical efficacy of this wheelchair-based approach: a moveable wheelchair arm rest device that promotes repetitive forward reaching practice. In our design sequence, experimenting with several prototypes, we solicited critical feedback from clinicians, culminating in the device we propose to test here. This movable wheelchair arm rest device is a novel wheelchair armrest that quickly clicks into a manual wheelchair frame just like a conventional armrest. However, unlike a conventional armrest, the device allows users to activate arm muscles in a way that is appropriate for the early stages of stroke recovery and consistent with the Feys et al. rocking chair approach: with biomechanical support of the shoulder, without high cognitive demand, and focusing on the “out-of-synergy” movement pattern that requires elbow extension. To achieve this, the movable wheelchair arm rest device incorporates an innovative linear mechanism that enables arm activation in two modes: 1) with the chair remaining stationary (“Stationary Mode”), or, 2) with the user contributing to propelling their wheelchair with their impaired arm (“Overground Mode”). Overground Mode transforms the “good arm + good leg” compensatory wheelchair propulsion technique into “good arm + good leg +

impaired arm” propulsion. Thus, the movable wheelchair arm rest device is a pragmatic tool for enabling individuals to activate the arm motor system during “wheelchair time”.

## **Provide relevant preliminary data (animal and/or human):**

From our previous work, we developed a novel lever-drive wheelchair, Lever Actuated Resonance Assistance (LARA), [10] that was designed to be used as a user’s primary wheelchair, thus enabling UE rehabilitation without sacrificing mobility, requiring a transfer, or requiring a separate device to be attached to the wheelchair before use. Specifically, Lever Actuated Resonance Assistance (LARA) allowed people to perform stationary UE rehabilitation in their wheelchair by moving attached levers back and forth with their impaired arm, or, after switching a manual switch, to propel their wheelchair bimanually with the levers. Using motion capture and EMG, we confirmed that persons with stroke achieved wheelchair propulsion by moving their impaired arm with normative biomechanics while activating elbow extension muscles. We tested LARA in a pilot, two-site randomized controlled trial with individuals with subacute stroke. We found that both stationary and overground exercise with LARA led to a significantly greater reduction in arm impairment than conventional treatment at a one month follow-up.

## **Describe the primary outcome variable(s), secondary outcome variables, and predictors and/or comparison groups as appropriate for the stated study objectives/specific aims:**

### **Primary outcome measure**

The primary outcome measure will be the change in Fugl-Meyer Arm Motor Assessment Score (FMAMA) from baseline to three-month post-stroke to assess increases in motor recovery of the upper extremity.

### **Secondary outcome measures**

Secondary outcome measures will include the change in:

1. Box and Block Test
2. Modified Ashworth Spasticity Scale for shoulder elbow and wrist joints
3. Shoulder subluxation distance in centimeters
4. Visual Analogue Pain scale to assess shoulder, elbow, wrist, and hand pain.
5. Motor Activity Log (MAL) – Post therapy and Follow-up assessments only
6. Functional Ambulation Category (FAC)
7. Number of exercise repetitions performed with device or exercise program.

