### Background & Purpose of Research

## Describe the purpose, specific aims or objectives and specify the hypotheses or research questions to be studied:

For this study, we hypothesize that use of movable wheelchair arm rest device during inpatient therapy will lead to significantly greater improvements in UE motor recovery than conventional treatment. (For a demonstration video of the movable wheelchair arm rest device, please visit: <https://youtu.be/RfbaOGhJfug>). Our Aim is to perform a randomized controlled trial of the movable wheelchair arm rest device with inpatients with subacute stroke in three different inpatient rehabilitation facilities (N=58; Months 6-24). UCI will be one of the study sites. Rancho Los Amigos Rehabilitation center and Casa Colina Hospital and Centers for Healthcare will potentially be the other two study sites. We are in the process of negotiating the contracts between sites. Participants will be >3 days and <3 weeks post-stroke, with initial FM scores <4239. Participants will be randomized to receive the movable wheelchair arm rest device or an electronic exercise program and instructed to practice moving their arm between therapy sessions. The primary outcome measure will be change in FM score from baseline to three-months post-stroke. We hypothesize that participants who receive movable wheelchair arm rest device will have significantly greater improvements in FM score than control ( $p < 0.05$ , RM-ANCOVA) without an increase in pain or spasticity, if they exceed the putative threshold of UE motor drive needed for recovery. Success Criteria: A significantly greater increase in FM of >4.25 points (the FM MCID40) between movable wheelchair arm rest device and control at three months.

At project end, we will have validated the clinical feasibility and efficacy of the movable wheelchair arm rest device and optimized it for production and mass distribution. If our plan is successful, we will have demonstrated that wheelchair-based "rocking therapy" can help patients routinely achieve the threshold level of sensory motor drive needed to provoke true UE recovery.

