## **Study Design & Statistics**

## **Include an explanation of the study design (e.g., randomized placebo-controlled, cross-over, cross-sectional, longitudinal, etc.) and, if appropriate, describe stratification/randomization/blinding scheme:**

This is a randomized controlled phase II clinical trial designed to test if use of movable wheelchair arm rest device reduces arm impairment compared to conventional training, in addition to standard rehabilitation therapy.

We will recruit individuals with an acute or subacute stroke from the Acute Rehabilitation Unit at UCI Medical Center to participate in this study. Participants will have arm impairment, which we will confirm with the Upper Extremity Fugl-Meyer Motor Assessment. After baseline evaluation, study participants will be equally randomized into two groups: device group versus control group. Randomization will proceed by block allocation based on time of enrollment.

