All study participants will receive 3 evaluations from a blinded evaluator: baseline at admission to the ARU, at discharge from ARU, and a 3-month post-stroke follow up visit.

Please see attachment for the schedule of study activities.

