## Provide a detailed chronological description of the procedures:

Participants will be invited for an initial assessment within three days of admission to an IRF to confirm they meet the inclusion criteria and to establish a baseline measure. Those who qualify will be randomly assigned to either the movable wheelchair arm rest device group or the control group. To ensure matched levels of impairment between groups, subjects will be stratified by their FM score into two levels (0-21, 22-42) and then randomized by alternating block allocation based on the time of enrollment. Individuals in the device group will be provided with a wheelchair equipped with movable wheelchair arm rest device and trained how to use it to perform stationary reaching practice and to help them ambulate. Once participants are competent, they will be instructed to perform stationary reaching practice and to use the movable wheelchair arm rest device to ambulate around the inpatient facility, with a target dose of 1000 device "reps" per day, which we estimate will take about 30 minutes of device use at around 1 rep every 2 seconds. The supervising therapist will customize the range of motion needed for device's integrated electronics to count a "rep" based on each patient's abilities. Participants in the control group will be given an electronic home exercise program (HEP) of proximal arm exercises developed by study therapists. They will be encouraged to exercise for 30 minutes a day with the electronic HEP (i.e. to match the duration with device). A supervising therapist will check in with all participants once per week to check on engagement with their exercise program and to troubleshoot any issues with device or the electronic exercise program. To measure compliance and quantify dose, the device will report the date, time, and number of repetitions completed for each movement type (stationary/overground) throughout the study using integrated electronics. Using technology, we previously developed for another study, the electronic exercise program provided to control participants will record how long the book is opened each day with a hidden magnetic sensor and data logger. Participants in both groups will continue therapy for the duration of their inpatient stays (average length of stay for individuals with moderate to severe impairment is 14 to 22 days, respectively, based on 104, n = 4142). The actual length of stay for each participant will be quantified and included as a covariate in the data analysis. Once participants are discharged, they will receive a post-therapy assessment and they may be allowed to keep the device and the exercise program based on the therapists' recommendations for the duration of the study. Participants will return three months following stroke onset for a final assessment. We would like to utilize the Tenovi Gateway device to collect the amount of use data. This data will be automatically uploaded to secure web portal through a Tenovi Gateway device, which plugs into the wall at subjects' rooms at the Acute Rehab Unit and or subjects' homes, automatically communicates with the exercise repetition counts through bluetooth, then uploads the data to the web portal through a low-speed cellular data connection. A study team member may visit participants' homes to set up the devices.

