
Boost is a novel arm rest that clips on a standard wheelchair with standard wheelchair features where anti-tipping bars in the back will prevent the wheelchair from tipping over. We have different sizes of the wheelchairs, 16", 18" and 20", to fit various patients according to their size and weight. We also have adjustable leg rests where we can fit patients with leg lengths or heights. We will have routine maintenance to make sure the wheelchairs operate well and are safe. For all study visits, we will have study personnel or nursing staff at the acute rehab unit present for the patients if patients need any help.

**Specify the total duration of a subject's participation in the study and clearly outline the duration of participation for each study visit and sub-study, as applicable:**

The duration of the subject's participation in the study will be approximately 3 months after the onset of stroke.

**List **all** data collection tools (e.g., measures, questionnaires, observational tool) below; include citations for standardized/validated measure(s):**

- Upper Extremity Fugl-Meyer Motor Score
- Box and Block Test
- Shoulder subluxation distance in centimeters
- Motor Activity Log (Post therapy and follow up assessments)
- Visual analog pain score for the shoulder and hand
- Modified Ashworth Spasticity Scale for elbow and wrist flexors and extensors
- Functional Ambulation Category (FAC)
- NIH Stroke Scale
- Number of exercise repetitions performed with device or exercise program
- Days of inpatient hospitalization stay
- Vital signs (heart rate, blood pressure)

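### The Motor Activity Log is listed as a change outcome but first measured at discharge, so its change captures only the between-arm difference arising after discharge

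*Combined protocol and SAP*

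**What the plan says.** Under Secondary outcome measures the list opens "Secondary outcome measures will include the change in", and the MAL is item 5 with the restriction "Post therapy and Follow-up assessments only". The list of data collection tools under Project Procedures repeats the restriction: "Motor Activity Log (Post therapy and follow up assessments". Two separate places agree, so it is not a slip.

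Study Design & Statistics gives three evaluations: "baseline at admission to the ARU, at discharge from ARU, and a 3-month post-stroke follow up visit". Project Procedures places the post-therapy assessment at discharge: "Once participants are discharged, they will receive a post-therapy assessment". Allocation comes earlier: "After baseline evaluation, study participants will be equally randomized into two groups". The first MAL score is therefore taken after randomization and after the inpatient training.

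The stated hypothesis is that "use of movable wheelchair arm rest device during inpatient therapy will lead to significantly greater improvements in UE motor recovery" than conventional treatment.

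On analysis, Study Design & Statistics names pain, spasticity and ambulation category for RM-ANCOVA. It does not name the MAL there. A general sentence under secondary analyses assigns a repeated-measures ANOVA to every outcome without saying which contrast is tested. Nowhere is the MAL change defined, given another reference value, or replaced by a comparison of scores.

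**The concern.** A change score normally removes pre-treatment differences. Here the reference value is itself affected by treatment, so the subtraction removes treatment effect instead.

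The MAL is the listed measure of use of the arm in daily life. If the device works during the inpatient stay and the gain is kept, the MAL change would show nothing. If the gain partly fades, or control participants catch up in part, the change would point towards control while the device arm was still better at 3 months. A reader of the results would have no signal that this came from the choice of reference visit.

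**Working it through.** The plan gives no figure for the MAL, so there is none to reproduce. The argument is algebra; the power figures only illustrate it.

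**What each contrast estimates.** Let b1 be the between-arm MAL difference at discharge and b2 the further difference arising by 3 months.

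- 3-month score: b1 + b2
- Change from discharge to 3 months: (b1 + b2) − b1 = b2

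The term b1 drops out whatever the SD, correlation or sample size. Randomization makes the 3-month comparison valid without a baseline MAL.

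**Examples, in SD units (assumed).**

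- Gain fully kept, b1 = 0.8, b2 = 0: the 3-month difference is 0.8 and the change difference is 0.
- Gain partly fades, b1 = 0.8, b2 = −0.3: the 3-month difference is 0.8 − 0.3 = 0.5 in favour of the device; the change difference is −0.3, in favour of control.

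**Power illustration.** Every input is an assumption except where a source is given.

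- The renewal form's Enrollment Status reports 22 + 15 = 37 adults. Less the 10% dropout assumed under Sample Size Determination, 37 × 0.9 ≈ 33, taken as 17 v 16. The number with MAL data is not stated.
- True 3-month difference 0.8 SD; SD 1 at each visit; two-sided alpha 0.05; noncentral t on 31 df.
- 3-month score: 0.8 / √(1/17 + 1/16) = 0.8 / 0.348 = 2.30, power 60%.
- Change: its SD is √(2(1 − r)), which is 1.000, 0.775 and 0.447 at r = 0.5, 0.7 and 0.9.

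| Share of 3-month effect present at discharge | Change estimates | Rejection rate, r = 0.5 | r = 0.7 | r = 0.9 |
|---|---|---|---|---|
| 50% | 0.40 | 20% | 30% | 70% |
| 80% | 0.16 | 7% | 9% | 17% |
| 100% | 0.00 | 5% | 5% | 5% |

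The bottom row is the nominal two-sided error rate, not power. At 50% and r = 0.9 the change rejects more often than the 3-month score (70% against 60%), yet it still estimates half the effect. At the planned size (29 per arm less 10%, about 26), power on the 3-month score is 81% and the bottom row stays at 5%.

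**Adjusting for discharge MAL does not help.** That analysis estimates b1 + b2 − r·b1. With b1 = 0.8 and b2 = 0 it gives 0.40, 0.24 and 0.08 at r = 0.5, 0.7 and 0.9.

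**The case against.** Three arguments deserve weight.

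*The list wording is loose.* The same stem covers item 7, the number of exercise repetitions, which has no pre-treatment value, so it cannot be literal throughout. The protocol also describes its primary outcome as a change in one place and as a 3-month score in another. This shows imprecise drafting. It does not supply another MAL definition, and an analyst following the list would compute the change.

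*The repeated-measures ANOVA could recover the effect.* Its group main effect averages the two visits and estimates b1 + b2/2. In the fully kept example that is 0.8, with power between 63% and 73% over the same correlations. This stands as far as it goes. But the plan names no contrast, and with two visits the group-by-time test is the change test. A reader might infer that the plan commits to group-by-time and therefore cannot detect an inpatient effect on the MAL. The documents do not support that; they leave the contrast open and do not override the change definition.

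*Treatment may continue after discharge.* Study Design & Statistics says participants will be allowed to keep the device or program until the 3-month visit; Project Procedures says they may be, on therapists' recommendation. Those statements need reconciling. Stays are short ("average length of stay for individuals with moderate to severe impairment is 14 to 22 days"). With enrollment between 3 days and 3 weeks post-stroke and 3 months taken as 91 days, roughly 91 − (21 + 22) = 48 to 91 − (3 + 14) = 74 days follow discharge. A reader might infer that the MAL change is meaningless or must be near zero. It is neither: it is a valid contrast for the post-discharge period, and near zero only if little further benefit accrues. It still excludes the inpatient effect that the hypothesis names.

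**Conclusion.** The point holds. As listed, the MAL outcome can only be a discharge-to-3-month change, and that change measures the between-arm difference arising after discharge. The loss equals whatever difference exists at discharge: none of the 3-month effect if all benefit comes later, all of it if the benefit is complete at discharge and kept. This follows from the measurement schedule alone. The power figures depend on an assumed effect, number analysed and correlation, and should be read only as a range.

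The scope is limited. The MAL is one of seven secondary outcomes. No success criterion or sample-size claim rests on it, and the primary Fugl-Meyer outcome has a baseline and is unaffected. The scores already collected support the better comparison, so no information has been lost.

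**What to change.** Take the MAL off the list of change outcomes. Define it as the between-arm comparison of the 3-month score, with the discharge score as supportive, both adjusted for baseline Fugl-Meyer and the Fugl-Meyer stratum (0–21, 22–42). State that discharge MAL is not a covariate. If the repeated-measures model is kept for the MAL, name the contrast. The discharge-to-3-month change may be reported as a description of the post-discharge period, labelled as such.

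The cost is a short wording change and no new data. There is a small downside: the renewal form's Enrollment Status and Progress Report say that procedures and follow-up are complete and analysis is under way. The change should therefore be dated, justified and disclosed, made before the MAL is compared by arm if possible, and labelled post hoc if that comparison has already been made.

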### Subject Population(s)

### Targeted subject populations/data sources (**check that apply**):

Adults Competent to Provide Informed Consent

Subjects who are unable to communicate in English

UCI Inpatients or Outpatients (Receiving Diagnosis/Treatment/Surgery)

## Sample Size

**Specify the maximum and expected numbers of individual-level information and/or biospecimens to be accessed/analyzed within each category/group.**

---

### **Category/Group**

Adults with Stroke

18-84

### **Maximum Number of Subjects, Subjects to be Consented or Reviewed/Collected**

30

Number Expected to Complete the Study or Needed to Address the Research Question

10

**Will this study take place only at UCI (i.e., does NOT involve other non-UCI sites)?**

No

**Overall Study Sample Size: Specify total number of subjects across all sites.**

58

## Sample Size Determination:

1. Explain how the overall target sample size was determined (e.g., power analysis; precision estimation). Power analysis should (at least) match the primary outcome/endpoint.
2. Provide justification of the effect size for the primary outcome based on preliminary data, current knowledge/literature and/or cost consideration.
3. If appropriate, provide sample size justification for secondary outcomes.

Based on a power analysis using data from our previous LARA RCT with individuals with subacute stroke (n=19)36, enrolling 29 participants in each group, brings a total of 58 from 2 groups, will provide an 80% chance to demonstrate a significant difference in FM between the device and control at the three-month follow up ( $\alpha = 0.05$ ), assuming a dropout rate of 10%.

---

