## Enrollment Status

### Accruals

**Please mark the option that represents the current status of subject enrollments:**

Enrollment and research procedures complete - only access to identifiable data / data analysis ongoing

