## Progress Report

### UCI Progress

**Please provide a detailed description of the progress of the study, including a brief summary of any interim findings or trends, and plans for the next approval period:**

We have completed our recruitment and enrollment for our study. All study procedures and follow up assessments have been completed. We are in the process of performing data analysis and manuscript preparation.

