**Provide any available information related to multi-center progress from the Sponsor:**

We are in the process of data analysis and will generate a final report and manuscript from the study.

---

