**Non-Technical Summary**

**Provide a non-technical summary of the project that can be understood by non-scientists (250 words max):**

Stroke is a leading cause of chronic disability with 6.8 million survivors currently living in the United States, and an annual cost over \$50 billion. An estimated 40% of people with a stroke live with moderate to severe impairment of their upper extremity [1-3]. One likely reason the percentage of people who end up with nonfunctional arms is so disappointingly high is that the number of arm movement repetitions provided as part of standard of care rehabilitation therapy is very small, especially early after stroke during their heightened period of brain plasticity. This is in part because practicing rehabilitative movements with a very weak upper extremity is difficult. There is a shortage of technologies that successfully address this problem of too low a dose of arm movement, especially among the large population of stroke survivors with more severe deficits. The goal of this study is to test a new lever drive movable wheelchair arm rest device that facilitates a person performing high amounts of practice with the severely impaired upper extremity (UE) during early stroke recovery. We will randomize a total of 58 individuals with a subacute stroke to exercise using a movable wheelchair arm rest device or receive additional conventional therapy during their inpatient stay, in addition to their normal rehabilitation. We hypothesize that the individuals who use the movable wheelchair arm rest device to exercise the arm will improve a measure of their upper extremity movement ability more than the control group as assessed at a follow-up evaluation.

---

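### The plan's 58 participants and 80% power do not describe the trial as conducted: 37 are reported enrolled, for which power is about 65% if the 80% held at the planned evaluable size

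*Combined protocol and SAP*

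**What the plan says.** **Plan.** Sample Size Determination bases the target on an earlier pilot RCT (n=19). It states that "enrolling 29 participants in each group, brings a total of 58 from 2 groups, will provide an 80% chance to demonstrate a significant difference". The outcome compared is the three-month FM score, with alpha 0.05 and "assuming a dropout rate of 10"%. It gives no effect size, SD or sidedness. The field headed "Specify total number of subjects across all sites" is answered 58. The Non-Technical Summary says "We will randomize a total of 58 individuals with a subacute stroke", and the purpose section repeats N=58. The success criterion there is "A significantly greater increase in FM of >4.25 points" between device and control, so statistical significance is part of it.

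**Conduct.** Enrollment Status gives 22 men and 15 women, 37 adults in all. It counts 2 participants since UCI approval, and the multi-center field gives 12 at Rancho Los Amigos and 23 at Casa Colina. The accrual status is "Enrollment and research procedures complete - only access to identifiable data / data analysis ongoing". UCI Progress says recruitment is finished and "All study procedures and follow up assessments have been completed". The multi-center progress field says "We are in the process of data analysis and will generate a final report and manuscript from the study".

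**Not given.** The document does not revise the target, restate power at the enrolled size or explain stopping below 58. It does not say how many participants in each arm have a 3-month FM score, although the modified intention-to-treat rule defines the analysis set by availability of follow-up.

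**The concern.** The sample-size section still presents 58 participants and 80% power while the status sections of the same document describe a trial that appears to have finished with 37. Because the success criterion requires significance, the chance of missing a real effect bears directly on how the result is read. At the planned power, a true effect of the planned size would be missed in 20% of trials; at the enrolled size the miss rate is higher. Someone who takes the design from the sample-size section would give a non-significant result more weight than 37 participants can support.

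**Working it through.** **1. Enrolment count.** By site: 2 + 12 + 23 = 37. Men: 22 − 10 − 10 = 2, so both UCI participants are men. Women: 15 − 2 − 13 = 0 at UCI. The totals reconcile, and the UCI entry of 2 does not conflict with 37. Fraction of plan: 37/58 = 63.8%.

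**2. The plan's own figure.** The 80% cannot be reproduced because the difference, SD and sidedness are not given. The dropout step can be checked: 29 × 0.9 = 26.1 evaluable per arm and, in reverse, 26/0.9 = 28.9, rounded up to 29. That step is correct.

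**3. Standardized effect implied by the plan.** Assume 80% power at 26 per arm, a two-sided 0.05 test and an unadjusted two-sample t-test. Power is P(|T| > t(0.975, df)), where T is non-central t with df = n1 + n2 − 2 and non-centrality d × √(n1·n2/(n1 + n2)). Solving at 26/26 gives d = 0.792. The normal approximation gives (1.960 + 0.842) × √(2/26) = 0.777.

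**4. Power at the enrolled size, same d.** The arm split is not reported; near-equal arms are assumed from the equal randomization. With 10% dropout, 37 × 0.9 = 33.3, or 33 evaluable.

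| Evaluable | n1/n2 | √(n1·n2/(n1+n2)) | Non-centrality | Power (t) | Power (normal) |
|---|---|---|---|---|---|
| Planned, 52 | 26/26 | 3.606 | 2.86 | 80% | 80% |
| All 37 | 19/18 | 3.040 | 2.41 | 64.9% | 65.6% |
| 33 | 17/16 | 2.871 | 2.27 | 59.6% | 60.7% |

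The miss rates are about 35% and 40%, against the planned 20%.

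**5. Effect detectable at 80% power (two-sided, t).** It is d = 0.792 at 26/26, 0.948 at 19/18 and 1.007 at 17/16. The ratios to plan are 1.20 and 1.27. The SD cancels, so the detectable FM difference is 20% or 27% larger than planned whatever the SD.

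**6. Sensitivity.**
- Arm imbalance with all 37 evaluable: 64.6% at 20/17 and 63.3% at 22/15, so modest imbalance matters little.
- If the 80% had been set at 29 evaluable per arm: 60.0% with 37 and 54.9% with 33. The stated dropout allowance supports 26.
- One-sided 0.05, which the documents do not state: 67.0% with 37 and 62.5% with 33.
- Covariate adjustment and Bonferroni correction, both named in the statistical sections, would shift these figures. The documents give neither the correlations nor the number of comparisons needed to compute by how much.

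**The case against.** The strongest reply is that nothing in the plan is wrong. A target and an accrual count sit in different fields and answer different questions, the counts are already disclosed, and a renewal filed without protocol changes would be expected to leave the sample-size text alone. Much of this stands. A reader might infer that the 80% is an arithmetic mistake. The documents do not support that, since the only checkable step is right and the inputs to the rest are absent. What the reply leaves open is that the shortfall, its reason and its effect on power are stated nowhere.

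A second reply is that 37 may not be final. The other sites' numbers are requested to date and if known, those sites have their own IRB approvals, and their closure is not stated. A reader might take closure at all three sites as documented. It is an inference, though the likelier reading, from the UCI report that recruitment for the study is complete and from the multi-center statement about analysis and a final report.

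Third, one might quote a single power range of 60–67%. That would mix two separate assumptions: the low end needs 10% dropout and the high end a one-sided test. The withdrawal section reports no removals or withdrawals (possibly for UCI only), and UCI reports follow-up complete. Both favour the all-evaluable, two-sided figure of about 65%.

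Finally, once results exist, the estimate and its confidence interval convey precision better than power does. That is fair, and the fix includes them. The calculation here uses the planned effect at the enrolled size, so it is not power computed from the observed result.

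**Conclusion.** The point holds as an undocumented gap between plan and conduct. The document states 58 and 80%, reports 37, and does not connect the two. Power for the planned standardized effect is about 65% if all 37 are evaluable and about 60% if the planned dropout occurred. The detectable difference is about 20% larger than planned, up to 27%.

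The power figures rest on 80% being right at 26 evaluable per arm, a two-sided 0.05 unadjusted t-test, near-equal arms and 37 being final. The shortfall in FM points cannot be given because the pilot effect size and SD are not shown. The count of 37 against 58 needs none of the power assumptions, but its finality depends on confirming closure at the two other sites.

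**What to change.** Keep 58 and 80%, labelled as the original plan. In the overall sample-size field and in Sample Size Determination, add a dated statement giving:

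- final enrolment: 37 of 58 (UCI 2, Rancho Los Amigos 12, Casa Colina 23), once closure at the other two sites is confirmed;
- the number in each arm with a 3-month FM score;
- the reason for closing below target;
- whether comparative results had been seen when the statement was written;
- the power, and the FM difference detectable at 80% power, at that size, using the pilot effect size and SD behind the original calculation.

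Report the estimated difference with its 95% confidence interval against 4.25 points, alongside the unchanged success criterion. Do not add a rule for how a non-significant result is to be interpreted: that would be a new commitment made during analysis, and the correction does not need it. The Non-Technical Summary, capped at 250 words, can stay as the plan.

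The cost is a small separate amendment, since this submission is a renewal without changes and the renewal instructions discourage major ones. It requires retrieving the pilot inputs and the per-arm counts. No further enrolment, new data collection or change of test is proposed. The downside is a less favourable stated power.
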